3.3.2 Secondary Endpoints

Clinical Endpoints:

- Time to alleviation of influenza clinical symptoms
- Time to absence of fever
- Time to resumption of normal activity
- Number of premature study treatment discontinuations
- Proportion of subjects who develop bronchitis, pneumonia, or other complications of influenza
- Proportion of subjects who require hospitalization
- 28-day mortality

Virologic Endpoints: (assessed by PCR in NP swab)

- Duration of viral shedding
- Change in viral shedding as a function of time
- AUC of viral shedding
- Frequency of emergence of antiviral resistance

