6.3.3.5 Distribution of Diary Cards

A diary card booklet assessing fever, symptoms, and functional assessment, will be distributed to subjects. Collection of baseline assessments and subject recalled pre-illness condition(s) (See Section 7.3.1) will be completed by the study team and instructions will be given to the subject on the completion of the diary card.

6.3.4 Day 1

Subjects will collect nasal specimen per the self-collection procedure described in Section 6.3.3.2, and will bring the specimen to the next study visit.

6.3.5 Day 2

Subjects will collect the nasal specimen per the self-collection procedure described in Section 6.3.3.2, and will bring the specimen to the next study visit.

6.3.6 Study Day 3

6.3.6.1 Clinical Data on Day 3

- Review and collection of diary card for fever, symptoms, and functional assessment (See Section 7.3.1)
- Assessment for presence of complications of influenza (See Section 7.3.2)
- Vital signs, including SaO₂ (See section 7.3.3)
- Review of study drug and assessment of compliance (see Section 7.5)

- Review of concomitant medications
- Symptom targeted physical exam (for safety assessment, see Section 7.1.2)
- Assessment for AEs

6.3.6.2 Research Procedures on Day 3

The following research procedures will be performed:

- Nasopharyngeal swab
- Subject sample self-collection as described in Section 6.3.3.2

See Section 7.3.4 for an overview of the planned virology assessments

6.3.7 Reference Laboratory Tests on Day 3

- Up to 20 mL of blood will be taken for the stored samples (see section 7.4)

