#### **4.8.2 Secondary Endpoints: Virologic Endpoints [IRCRSLTS] (PEP and ITT)**

Viral shedding will be assessed by quantitative RT-PCR (reported as  $\log_{10}$  RNA copies/mL) with measurements obtained on Days 0, 3, and 7. These measurements will be used to define the following variables:

- a. Figure and associated table showing number (%) of subjects who had values  $<LOD$ ,  $LOD-<LLOQ$ ,  $\geq LLOQ$  at each visit.
- b. Figure and associated table showing number of subjects and minimum, maximum, median, 25% and 75% percentile of the value of viral shedding at each visit (subjects with values  $<LOD$  will be ranked as lower than detectable values in this analysis; minimum and maximum in table only). Comparison of randomized arms at each of Day 3 and Day 7 will be based on the extension of Wilcoxon's test to handle censoring of measurements which are  $<LLOQ$ .
- c. Number (%) of subjects with undetectable viral load at both Day 3 and Day 7; detectable at Day 3 and undetectable at Day 7; detectable at Day 7 (irrespective of whether or not detectable at Day 3). Analysis will be restricted to subjects with measurements at both Day 3 and Day 7. Comparison of percentages of subjects in this table using the Wilcoxon Test.
- d. Above tables/figures/analyses will be repeated for the subset of subjects who had detectable viral load at Day 0.

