#### **4.10 Evaluation of self-collected samples (PEP and ITT)**

Self-collected NP are collected on Day 0 (prior to treatment initiation), Day 0 evening, Day 1, Day 1 evening, Day 2, Day 2 evening and Day 3. Viral shedding will be assessed using these self-collected swabs by the same assay used for the team collected swabs, i.e., quantitative RT-PCR (reported as  $\log_{10}$  RNA copies/mL).

- a. Completeness of viral shedding results showing number (%) at Day 0, Day 0 evening, Day 1, Day 1 evening, Day 2, Day 2 evening and Day 3 who:
  - had swab taken (i.e. submitted)
  - had qPCR result
  - died prior to visit
  - were lost to follow-up prior to the visit
  - were in follow-up but had missing value
- b. Among subjects with Day 3 qPCR results, number (%) with detectable viral shedding at Day 3. Comparison of randomized arms with associated 95% confidence interval and p-value based on the normal approximation to the binomial distribution. This table can be compared to table 4.8.1a, the primary endpoint, to determine if the self-swabs would have similar treatment effects
  - Repeat analysis in the population for the primary analysis (PEP excluding pilot study) to allow direct comparison with primary endpoint.
- c. Bland-Altman plot showing the agreement between the result from the self-collected swabs and team-collected swabs across all available swabs
- d. Bland-Altman plot showing the agreement between the result from the self-collected swabs and team-collected swabs on Day 0 and Day 3.
- e. Table: Mean, standard deviation, median, min, max, 25% and 75% percentiles of the viral load difference between self-collected swabs and team-collected swabs on Day 0, Day 1, Day 2 and Day 3. P-values comparing the difference based on normal approximation or Wilcoxon signed rank test, as appropriate for the data.
- f. Plots of associations between viral load based on self-collected swabs and viral load based on team-collected swabs on Day 0, Day 1, Day 2 and Day 3. Spearman correlation coefficients, along with their 95% confidence intervals, will be provided. Plots of associations and estimated correlation coefficients will be provided both over all subjects and by strata defined by quartile of the viral load based on team-collected swabs at each time point.

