- g. AUCs will be calculated for the self-collected swabs. This is defined as the area below the line formed by joining the measured values at each successive scheduled measurement time and above the limit of detection. This will be calculated using the trapezoidal rule. Missing values will be ignored (this is equivalent to imputing a missing value using linear interpolation between the previous and succeeding available values). If the Day 0 value is missing, then the subject will be excluded from the analysis.
  - Figure and associated table showing number of subjects and minimum, maximum, median, 25% and 75% percentile of the value of viral shedding at each scheduled measurement time. This will be presented (a) imputing values

as defined above for the calculation of AUC, and (b) using observed values only.

- Table showing number of subjects and minimum, maximum, median, 25% and 75% percentile of the AUC, both over all subjects and by strata defined by quartile of Day 0 measurement.
- P-value comparing randomized arms from Wilcoxon rank sum test stratified by quartile of Day 0 measurement.

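### The self-swab AUC in SAP 4.10g has no sound rule for missing last swabs: taken literally, the area stops early and can only come out equal or smaller

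*SAP*

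**What the plan says.** SAP 4.10 item g defines the AUC as "the area below the line formed by joining the measured values at each successive scheduled measurement time and above the limit of detection", calculated by the trapezoidal rule. On missing data it states: "Missing values will be ignored (this is equivalent to imputing a missing value using linear interpolation between the previous and succeeding available values"). The only exclusion is: "If the Day 0 value is missing, then the subject will be excluded from the analysis". It does not require a final swab, set a minimum number of swabs, rescale to a common time span or plan a sensitivity analysis.

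The result is tested between arms: "P-value comparing randomized arms from Wilcoxon rank sum test stratified by quartile of Day 0 measurement".

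After the pre-treatment swab, the SAP 4.10 schedule runs "Day 0 evening, Day 1, Day 1 evening, Day 2, Day 2 evening and Day 3", which makes seven time points in all. Protocol 3.1 and 7.3.4.5 give one self-swab a day on Days 0 to 3, which makes four. Under Protocol 6.3.4 and 6.3.5, a subject who takes a swab at home "will bring the specimen to the next study visit". The Day 3 self-swab is listed among that visit's procedures (Protocol 6.3.6.2), and the first self-swab is taken in the clinic with staff present (Protocol 6.3.3.2).

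Protocol 3.3.2 lists "AUC of viral shedding" among the virologic secondary endpoints, all assessed by PCR in NP swab. SAP 4.8.2 works from NP data "with measurements obtained on Days 0, 3, and 7" and derives no AUC in items a to d.

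**The concern.** Interpolation needs a value on each side of the gap. A missing last swab has a value on one side only, so the SAP's description of what its rule does is wrong there. A literal program joins the values that exist and stops. Subjects are then compared on areas that span different lengths of time, and a short area looks like fast clearance.

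Loss at the end of the series is a plausible pattern here. The Day 0 swab is secured in the clinic, while the home swabs depend on a later visit. A missed Day 3 visit may therefore remove several swabs together and leave Day 0 in place, and Day 0 is all that item g requires.

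At stake are the AUC summaries and the p-value comparing arms on self-swabs. That p-value is part of judging whether self-swabs can measure a treatment effect.

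**Working it through.** The documents give no figure for this AUC, so the check is of the SAP's equivalence statement and of what follows when it fails. All viral-load paths and loss rates below are assumptions. Loads are in log10 above the limit of detection (LOD) and areas are in log10-days.

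**1. Interior gaps: the statement is right.** Assumed loads of 4, 4.2, 3.9, 3.1, 2.8, 2.0, 1.5 at days 0, 0.5, …, 3 give a full area of 0.5 × (4/2 + 4.2 + 3.9 + 3.1 + 2.8 + 2.0 + 1.5/2) = 9.375. With Day 1 missing, ignoring it and interpolating both give 9.25. With days 0.5, 1 and 2 missing, both give 8.75.

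**2. Trailing gaps: the statement fails.** On the same path, losing the last swab gives 8.5 and losing the last two gives 7.3, because the area ends at the last observed time.

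On the simpler path 4, 3, 2, 1 on Days 0 to 3, the daily trapezoids are (4+3)/2 = 3.5, (3+2)/2 = 2.5 and (2+1)/2 = 1.5.

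| Swabs available | Area | Change from full |
|---|---|---|
| Days 0–3 | 3.5 + 2.5 + 1.5 = 7.5 | none |
| Days 0–2 | 3.5 + 2.5 = 6.0 | −20% |
| Days 0–1 | 3.5 | −53% |
| Day 0 only | no segment: 0 or undefined | – |

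Area above the LOD cannot be negative, so cutting the series short can only lower the total or leave it unchanged. It is unchanged only if the subject is at or below the LOD from the last swab on.

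**3. Ranks can reverse.** A subject constant at 4 who stops after Day 1 gets 4 × 1 = 4. A fully sampled subject who falls linearly from 4 to 0 by Day 3 gets (4 + 0)/2 × 3 = 6. The constant shedder ranks as the better result.

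**4. The analysis window.** SAP Table 1 widens Day 3 to 3±1. A Day 4 swab can therefore fill the Day 3 slot. The window also reaches back to Day 2, and if a Day 2 swab were used for a missing Day 3, the second row of the table would become 3.5 + 2.5 + 2.0 = 8.0. The SAP does not say whether this applies to the AUC.

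**5. Effect on the test.** These are simulations with no treatment effect, 250 per arm, the Wilcoxon test stratified by Day 0 quartile, and two-sided 5%. Loss is random within arm.

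Four-point schedule (Day 0 mean 4, SD 1.5; decline 1 per day, SD 0.5; noise SD 0.5):

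| Loss in the two arms | Day 0 only, scored 0 | Stops after Day 1 | Stops after Day 2 | Subjects excluded |
|---|---|---|---|---|
| 10% v 10% | 5% | 5% | 4% | 5% |
| 13% v 7% | 22% | 16% | 7% | 4% |
| 15% v 5% | 47% | 33% | 12% | 5% |

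Seven-point schedule (Day 0 mean 4, SD 1.2; decline 0.8 per day, SD 0.5; noise SD 0.5):
- Day 0 only, scored 0: 5% (10% v 10%), 17% (5% v 10%), 47% (5% v 15%). Excluding these subjects gave 4% to 6%.
- Last swab spread over the schedule: 5% (10% v 10%), 10% (5% v 10%), 28% (5% v 15%).
- Equal 10% loss with one assumed real effect (decline faster by 0.12 per day): power about 37% when those subjects score 0, and about 45% when they are excluded.

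**6. Limits of exclusion.** If the losses in one arm were assumed to fall among slow decliners, excluding them on the four-point model gave null rejection of about 36% (15% v 5%) and 27% (13% v 7%). The size depends on how strongly loss is tied to viral decline.

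**The case against.** Several counter-arguments have force.

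- **The SAP does not score these subjects as zero.** A reader might infer that a subject with Day 0 alone receives the best possible AUC by rule. Item g does not say so: one point forms no line, and zero is what a literal trapezoid program would return. This stands. The result is zero or undefined, and the SAP does not settle which.
- **This is not the listed endpoint.** Because item g is the only AUC the SAP derives, a reader might infer that a named secondary endpoint is compromised. The protocol's endpoint is the NP-swab AUC, and section 4.10 evaluates self-swabs. The absence of an NP-swab AUC from SAP 4.8.2 is a separate matter.
- **Total loss is not certain.** Missed visits are to be rescheduled (Protocol 4.8), home visits are allowed (Protocol 6.1), and a Day 4 swab falls inside the window. Home swabs might still arrive at a later visit, and the documents do not void them. This makes the loss smaller but does not remove it.
- **The large error rates are chosen.** No document supports 15% v 5% total loss. The 10% in Protocol 9.2.1 concerns missing Day 3 qPCR in the primary-endpoint sample size, and it includes handling and assay problems that need not remove every later swab. With mild imbalance the effect is small: 11% v 9% gave about 6%, and 12% v 8% gave about 11%.
- **Missingness will be visible.** The completeness table in 4.10a and the observed-values table in 4.10g would show an imbalance. Neither corrects the AUC or its test.

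None of this rescues the equivalence statement for trailing gaps.

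**Conclusion.** The defect holds. The stated rule is correct for interior gaps and wrong for trailing ones. Taken literally, it shortens the area (7.5 to 6.0 or 3.5 in the example, provided the Day 2 swab is not moved into the Day 3 slot) and carries that value into a between-arm p-value with no sensitivity analysis.

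With equal loss in the two arms the type I error stays near 5%, and the cost is distorted summaries and lower power. With unequal loss the comparison can be biased in favour of the arm that loses more swabs. The size is not known in advance: about 5% to 47% null rejection over the assumed scenarios, with the top of that range needing a threefold difference in total loss. It should not be read as the expected false-positive rate of this trial.

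The primary endpoint and the listed NP-swab AUC are not affected. The correction should be made, because otherwise the programmer must choose a rule that can change the p-value.

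**What to change.** In SAP 4.10g:

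1. Limit the ignore-missing rule to interior gaps, where a later value exists.
2. Require a Day 0 value and a value for the Day 3 time point. Accept a late swab (Day 4) under the 3±1 window, and state that a Day 2 swab does not stand in for Day 3 in the area. A requirement for a swab on exactly Day 3 would conflict with SAP Table 1.
3. Exclude subjects without that terminal value from the main AUC comparison. Do not let any area end early.
4. Add a sensitivity analysis that includes them, for example with the last observed value carried to Day 3. Exclusion alone is unbiased only if loss is unrelated to viral load within arm.
5. Report by arm the number excluded for a missing terminal value.

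The cost is a few sentences of SAP text, a few lines of code and a slightly smaller AUC analysis set. No change to data collection is needed.

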#### **4.11 Emergence of antiviral resistance. (ITT)**

Due to technical demands and cost of sequencing, resistance will be evaluated only in subjects that have virus present at Day 7, i.e., subjects that stop viral shedding by Day 7 will be considered as not having clinically significant resistance. All subjects with virus isolated at Day 7 will have Day 0 and 7 samples evaluated by DNA Sequencing (Sanger method) of M2, NA and HA genes. As this is primarily descriptive data of genetic sequences, and not statistical analysis, this data will be presented in a separate report.

- a. Number (% of subjects with Day 7 measurement) of subjects with detectable viral shedding at Day 7.
- b. The number (% of number) of subjects with samples sequenced.
- c. The number (% of number) of subjects with detectable viral load, but were not sequenced as the viral load was near the limits of quantification (suggesting resistance is unlikely).
- d. Listing, separated by strain (H1N1, H3N2, and B) of subject ID, study day, viral load, amino acid substitutions tested (those known to convey amantadine or oseltamivir resistance), amino acids detected in the sample at the given position.
- e. Interpretation if any amino acid substitutions detected are likely to confer resistance (based on literature review).
